4.1.3 Post-operative phase & follow-up

Within 24h after surgery the patient will undergo a CT-scan to assess the position of the newly-placed drain. The primary endpoint, accuracy of drain placement evaluated on the immediate postoperative CT and graded according to clinical relevance, will be evaluated using the abovementioned Kakarla scale (*Table 2-1*).

In the further post-operative period, the patient's status will be monitored as it would be for every patient undergoing standard treatment for the abovementioned pathologies: in the immediate post-operative phase the patient is monitored in the Intensive Care Unit (ICU). In the following days the patient may undergo additional imaging of the brain if deemed necessary, and his/her clinical status will be continuously monitored, as is common practice. Based on the clinical evolution, the drain may or may not be removed, and the patient may or may not be transferred to the neurosurgical ward.

As soon as the patient is deemed adequately fit, he/she will be discharged from the hospital and a first follow-up appointment will be planned after 6 weeks. At this appointment the patient's clinical status and cranial imaging status will be assessed one final time, after which the patient has completed his/her participation in the trial.

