4.4 Life Style Guidelines

The use of the HoloLens does not interfere with the patients’ life style. Lifestyle adjustments will therefore only be adjusted if necessary based on the requirements for the planned surgical procedure. This includes the standard period of post-operative care and follow-up.

5 Statistical design

This is a class II, single-arm, clinical pilot study investigating feasibility, safety and efficacy of a proprietary software solution for augmented reality-display, and registration and tracking of patient-specific anatomic models on the Microsoft HoloLens (further referenced to in this paragraph as “the experimental treatment”) in patients requiring EVD placement.

A patient is considered evaluable if he has signed informed consent and has undergone the HoloLens-assisted surgical intervention. Primary endpoint is accuracy according to the abovementioned Kakarla scale and can be evaluated within 24 hours after surgery. Patients will be encouraged to complete follow-up (which does not differ from standard follow-up for these pathologies) in order to evaluate the secondary endpoints (clinical outcome, cfr below) but will remain evaluable in the context of the trial even if planned follow-up has not been completed.

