5.4 Statistical analysis

Dichotomized comparisons will be used to compare drain placement accuracy performed with versus without surgical AR assistance. Results obtained from the Kakarla scale after surgery with the AR guidance will be tabulated and compared to historical values obtained from literature and from our institution. These historical values are based on previous research in drain placement (without the use of AR guidance), and will be matched with the cases of the current study.

To achieve these dichotomized comparisons, we will use cut-offs within the accuracy scale to define different benchmarks of good versus bad drain placement. The cut-off can be placed at either side of the 'suboptimal placement'-category (cfr. Part 1), depending on the degree of accuracy we wish to pursue: a comparison with the cut-off above this category will analyze the improvement of perfect placement, whereas the cut-off below this category will analyze acceptable drain placement in general. Given the eventual alternating hypothesis of increased placement accuracy related to the use of AR guidance, along with the small expected sample size, these comparisons will be performed through one-sided Fisher's exact tests.

6 Patient registration procedure

Prior to undergoing any study-specific procedure, patients must read the patient information brochure and sign the current **Institutional Review Board** (IRB)-approved IC form (see Part 10.3 for the procedure during emergency situations). Screening procedures can then take place as listed in Part 4. Subjects meeting the eligibility criteria for study participation will start experimental treatment as soon as is estimated possible by the investigator.

Patient withdrawal

A patient may withdraw from the trial at any time at their own request, or they may be withdrawn at any time at the discretion of the investigator or sponsor for safety, behavioral, or administrative reasons. Unless the subject specifically withdraws his consent for use of the obtained data, the patient will remain evaluable within the trial if he has undergone the AR-assisted surgical procedure since the primary endpoint and some secondary endpoints are based on results that are obtained immediately after the surgical intervention.

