If a subject does not return for the scheduled follow-up visit, every effort should however be made to contact the subject and to document subject outcome, if possible. If the subject withdraws consent, no further evaluations should be performed and no attempts should be made to collect additional data, and the data obtained until that point will not be used in the final analysis.

A patient may be withdrawn from the trial in case the surgical intervention cannot be performed for any reason (for example sudden unexpected adverse event preceding the surgery and precluding it), or in case of withdrawal of patient consent

7 Forms and procedures for collecting data

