7.4 GDPR-compliancy

In accordance with the recent installment of the **General Data Protection Regulation** (GDPR) on the 25th of May 2018, following measures will be taken:

- All personal data of the participating patients will be processed by the PI of this study or anyone working directly under his supervision.
- To ensure protection of all personal data during processing, a **Data Protection Officer** (DPO) ([contact]) will be appointed.
- The gathered data will only be used to investigate the endpoints mentioned in this protocol under **5.1 Objective & endpoints**. As mentioned before, a patient may withdraw his consent for the use of any previously obtained data at any time. This withdrawal requires no justification from the patient, nor will it have any influence on the quality of the provided care.
- The only investigators with access to personal data are investigators with a medical background (physicians) and physicians caring for the patient. All other involved parties and investigators will only be able to view anonymized data (see Part 10).
- There will be no transfer of personal data to any other countries.
- All personal data will be retained as explained above in Part 7.2.

8 Reporting adverse events

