10.3 Informed consent

The IC form must be agreed to by the IRB/IEC and must comply with the International Organization for Standardization GCP, local regulatory requirements, and legal requirements. The IC form used in this study, and any changes made during the course of the study, must be prospectively approved by the IRB/IEC before use.

The investigator must ensure that each trial subject, or his/her legally acceptable representative, is fully informed about the nature and objectives of the trial and possible risks associated with participation. The investigator will try to obtain written IC from each subject or the subject's legally acceptable representative before any study-specific activity is performed. The investigator will retain a copy of each subject's signed consent form.

In emergency situations, however, the study treatment must be started as soon as possible after the patient is admitted to the hospital. In these situations, the patient is usually unable to decide for him-/herself whether or not to take part in the study. Waiting until the legal representative arrives to inform him/her of the study and obtain his/her consent for the participation of the patient he/she represents would mean the normal urgent care has to be provided and the investigational treatment can no longer be offered under these conditions. Since a patient's participation will most likely benefit the progress of his/her clinical situation under these specific conditions, we will therefore implement the investigational treatment both without the consent of the patient and without the consent of the legal representative, in accordance with the provisions of Chapter VI of the Law of May 2004 related to experiments on humans.

The consent of the legal representative will be obtained as soon as possible and the patient's consent will be asked once the improvement in his/her clinical situation allows him/her to be informed correctly of the objectives and procedures of the study and to agree to them. If the patient (or legal representative) does not give his/her consent, the previously obtained data cannot be used for further analysis. All decisions and informed consent procedures during this emergency situation will be well documented, dated (date & time) and signed by the investigator in charge.

11 Trial sponsorship and financing

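### The withdrawal rules in section 6 disagree for a treated patient who withdraws consent to take part without mentioning data already obtained, so a known placement grade may be kept or excluded

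*Combined protocol and SAP*

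**What the plan says.** Section 6, under Patient withdrawal, lets a patient leave the trial at any time. For patients who have had the AR-assisted procedure it then states: "Unless the subject specifically withdraws his consent for use of the obtained data, the patient will remain evaluable within the trial". The reason given is that the primary endpoint and some secondary endpoints are obtained immediately after surgery.

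The next paragraph of the same section first deals with patients who do not return for the visit; they are to be contacted and their outcome documented if possible. It then says: "If the subject withdraws consent, no further evaluations should be performed". No attempt is to be made to collect additional data, and "the data obtained until that point will not be used in the final analysis".

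Four other places bear on this:

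- Section 5 (Statistical design): the primary endpoint "can be evaluated within 24 hours after surgery", and a treated patient "will remain evaluable in the context of the trial even if planned follow-up has not been completed".
- Section 4.1.3: after discharge, "a first follow-up appointment will be planned after 6 weeks". That visit ends participation.
- Section 7.4: "a patient may withdraw his consent for the use of any previously obtained data at any time". Consent to data use is treated here as an act of its own.
- Section 10.3: if consent is refused after emergency inclusion, "the previously obtained data cannot be used for further analysis".

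**The concern.** The first rule in section 6 is triggered by withdrawal of consent for data use. The second is triggered by withdrawal of consent without qualification. A patient who says that he no longer wishes to take part, and is silent about his scans and grade, meets the second trigger but not the first. He is in the analysis under one paragraph and out of it under the next.

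The Kakarla grade exists within a day of surgery and the patient can withdraw for weeks afterwards. The choice between the two rules could therefore be made when the grade is already known. If withdrawals were more common after a poor placement or a complication, applying the second rule would raise the observed accuracy. With 10 to 15 patients, one exclusion moves the rate visibly.

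**Working it through.** The plan gives no figure for withdrawal, so the first step is to compare the rules case by case.

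| Treated patient | Section 6, first paragraph on withdrawal | Section 6, following paragraph | Agree? |
|---|---|---|---|
| Misses or declines the follow-up visit, consent stands | Kept | Kept; contact attempted | Yes |
| Specifically withdraws consent for data use | Excluded | Excluded | Yes |
| Withdraws consent to take part, silent on existing data | Kept | Excluded | **No** |

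Section 5 concerns incomplete follow-up, which is the first row, so it conflicts with neither paragraph. Section 10.3 concerns a patient included in an emergency whose consent is later refused. That is a separate ground for exclusion and is not in dispute.

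The second step is an illustration of what one exclusion can do.

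**Inputs from the documents:** 10 to 15 patients (section 5.2); one-sided Fisher's exact test on a dichotomised scale (section 5.4); freehand good placement of 77 to 79% (section 1.3); null accuracy of 70 to 80% (section 5.2).

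**Assumptions:** the cut-off is good placement against the rest; the control rate is 78%, the midpoint of 77 to 79%; the excluded patient is the only one without good placement. The documents give no number of controls, so it is varied.

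**Formula:** with the margins fixed, the number of good AR placements X is hypergeometric, and p = P(X ≥ observed).

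With 156/200 controls and 14/15 AR patients there are 170 good placements among 215:

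p = [C(170,14)·C(45,1) + C(170,15)] / C(215,15) = 0.1115 + 0.0258 = 0.137.

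With the non-good patient excluded there are 170 good placements among 214:

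p = C(170,14) / C(214,14) = 0.036.

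The same calculation over a range of controls:

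| AR result, all kept → one excluded | Controls | p, all kept | p, one excluded |
|---|---|---|---|
| 14/15 → 14/14 | 39/50 | 0.169 | 0.0502 |
| 14/15 → 14/14 | 78/100 | 0.148 | 0.040 |
| 14/15 → 14/14 | 156/200 | 0.137 | 0.036 |
| 14/15 → 14/14 | 390/500 | 0.131 | 0.033 |
| 14/15 → 14/14 | 80/100 | 0.19 | 0.056 |
| 9/10 → 9/9 | 156/200 | 0.33 | 0.11 |

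The observed rate goes from 93.3% (exact 95% interval 68.1 to 99.8%) to 100% (76.8 to 100%) when 14/15 becomes 14/14. It goes from 90% to 100% when 9/10 becomes 9/9.

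**The case against.** The best defence is that the two paragraphs stand under one heading and can be read together: the consent meant in the second is the data-use consent just named in the first. On that reading nothing conflicts. It is possible but weak. The same sentence stops further evaluations and further data collection, which are consequences of ending participation. The section's closing paragraph lists withdrawal of patient consent as a ground for leaving the trial. Where the protocol means data use, in section 6 and again in section 7.4, it says so. Even if the narrow reading is intended, the text needs to state it.

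Several other objections stand in full, and each rules out something a reader might infer:

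- *That a patient who merely declines follow-up loses the primary outcome.* Non-return is handled separately, and such a patient stays in.
- *That data are deleted.* The text says only that they are not used in the final analysis; section 7.2 keeps records for 20 years.
- *That selective withdrawal will occur.* The documents give no withdrawal rate. The remark in section 5.2 that dropout is unlikely concerns cancelled surgery, so it settles the matter neither way.
- *That one exclusion makes the trial significant.* This happens only near 15 patients with favourable assumed controls. At 10 patients, or against 80/100, it does not.

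It is also fair to say that this is a feasibility study, with the formal comparison left to a later, larger trial, and that section 5.3 undertakes to account for all registered patients. However, the withdrawals that section 5.3 names are those before treatment began. A treated patient excluded later would appear, at most, in the general count of patients who were not evaluable.

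**Conclusion.** The point holds for one defined case. When a treated patient withdraws consent to take part and does not mention existing data, section 6 gives two opposite instructions, and one of them drops a primary outcome already recorded. It also defeats the protocol's own reason for retention, that the endpoint is available right after surgery.

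The effect may be nil if no such withdrawal occurs. If one does, and it is the only non-good placement, the observed rate rises by 6.7 percentage points at 15 patients (93.3% to 100%) or 10 points at 10 patients. Whether the nominal test crosses 0.05 depends on the final sample size and on a control rate and control count that are assumed here. The conclusion rests on reading the second trigger as written, without the unstated limit to data use. It does not rest on the p-values.

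**What to change.** Amend the second withdrawal paragraph of section 6 so that it agrees with the first and with section 7.4. It should say that on withdrawal from participation no further data are collected, and that data already obtained from a treated patient stay in the analysis unless (a) consent for data use is specifically withdrawn or (b) deferred emergency consent is refused under section 10.3. Ground (b) must be named, because a rule that allowed exclusion only on ground (a) would contradict section 10.3.

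Check that the consent form makes the same distinction. It was not available for this review, and neither was the applicable law, so the sponsor should confirm that retention is permitted as worded.

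Extend section 5.3 to report the number of treated patients excluded on each consent ground.

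The cost is about one sentence in section 6, a short addition to section 5.3 and a check of the consent form. No design change or extra data collection is needed.

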7.1 Case Report Forms / Electronic Data Record

As used in this protocol, the term eCRF should be understood to refer to an electronic data record (Excel and Microsoft Access file). This eCRF will be completed for each included subject. The completed original eCRF is the sole property of the study sponsor (UZ Brussel) and will not be made available in any form to third parties, appropriate regulatory authorities, without written permission of the UZ Brussel.

It is the investigator's responsibility to ensure completion and to review and approve all eCRF data. At all times, the investigator has final personal responsibility for the accuracy and authenticity of all data entered on the eCRFs.

Subject source documents are the physician's subject records maintained at the trial site. In most cases, the source documents will be the hospital's or the physician's chart or a study chart. The source documents must match the information collected on the eCRF.

7.2 Record Retention

To enable evaluations and/or audits from regulatory authorities, the investigator agrees to keep records, including the identity of all participating subjects (sufficient information to link records, e.g. eCRFs and hospital records), all original signed IC forms, copies of all eCRFs, source documents, and detailed records of treatment disposition. The records should be retained by the investigator according to local regulations during a period of 20 years.

7.3 Study Monitoring

This study will be initiated as a single center study. During the conduct of this study at a single site (UZ Brussel), the sponsor will monitor for the completeness and accuracy of the eCRF content.

7.4 GDPR-compliancy

In accordance with the recent installment of the **General Data Protection Regulation** (GDPR) on the 25th of May 2018, following measures will be taken:

- All personal data of the participating patients will be processed by the PI of this study or anyone working directly under his supervision.
- To ensure protection of all personal data during processing, a **Data Protection Officer** (DPO) ([contact]) will be appointed.
- The gathered data will only be used to investigate the endpoints mentioned in this protocol under **5.1 Objective & endpoints**. As mentioned before, a patient may withdraw his consent for the use of any previously obtained data at any time. This withdrawal requires no justification from the patient, nor will it have any influence on the quality of the provided care.
- The only investigators with access to personal data are investigators with a medical background (physicians) and physicians caring for the patient. All other involved parties and investigators will only be able to view anonymized data (see Part 10).
- There will be no transfer of personal data to any other countries.
- All personal data will be retained as explained above in Part 7.2.

8 Reporting adverse events

8.1 Safety Monitoring

Adverse events will be monitored on an ongoing basis and their frequencies reported semi-annually. The worst event for each patient will be described. Both events related and unrelated to treatment will be captured. Clinical outcome data will be tabulated and compared to normal ranges for the institution, based on historical values obtained at the institution.

8.1.1 Adverse events

All observed or volunteered adverse events regardless of suspected causal relationship to the investigational product(s) or intervention will be reported as described in the following sections. For all adverse events, the investigator must pursue and obtain information adequate both to determine the outcome of the adverse event and to assess whether it meets the criteria for classification as a serious adverse event (cfr. below) requiring immediate notification to the study sponsor / IRB / **Internal Ethics Committee** (IEC). For all adverse events, sufficient information should be obtained by the investigator to determine the causality of the adverse event. The investigator is required to assess causality. For adverse events with a causal relationship to the investigational product, follow-up by the investigator is required until the event or its sequelae resolve or stabilize at a level acceptable to the investigator.

As the use of the HoloLens has no direct impact on the workflow of the standard surgical procedure, we do not expect it to cause any adverse events whatsoever. We expect general surgery-related complications as they would happen in the standard of care for the abovementioned pathologies, but none of these complications are directly linked to the use of the device.

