4.1.2 Operative phase

The procedure itself will take place in a standardized fashion, performed by surgeons (in this case neurosurgeons or neurosurgeons in training) of different expertise levels (but always with adequate expertise and clearance to perform this procedure, as is current clinical practice). Surgical technique for the procedure is described below. The main difference is the use of the HoloLens as an AR device for visual aid during the procedure, which will not alter the operational workflow. The HoloLens will only be used immediately before and during the planned surgical procedures.

Surgical technique

The patient is installed on the operating table in the supine position. Patients will be sedated. The entry point is decided by the surgeon (usually at Kocher's point), based on the pathology at hand, pre-existing anatomical knowledge and knowledge of anatomical landmarks, but also surgical planning information based on the preoperative CT scan, as well as the augmented reality-displayed surgical trajectory. The entry point is then marked on the skin (after local shaving if necessary) and the patient undergoes standard surgical prepping (disinfection) and draping. A stab incision is made at the entry point, after which the hand drill is placed against the skull and a drill trajectory is made in the skull, following the predefined trajectory that the drain should follow. This trajectory is based, again, on the pathology at hand, pre-existing anatomical knowledge and knowledge of anatomical landmarks and trajectories, surgical planning information based on the preoperative CT scan, and, importantly, the augmented reality-displayed surgical trajectory. The drain is then placed through the drill hole and advanced until the predefined depth (decided upon based on the surgical planning). After placement, flow of CSF or blood (depending on the pathology) through the drain is checked, after which it is secured to the skin with suture thread and connected to a drainage system.

Analysis

The following measures pertaining to the surgical experience will be recorded during and after the surgical procedures:

- Duration of the surgical procedure (in minutes)
- Number of passes of the drain before correct placement
- Surgeon's estimate of success of placement (using the graded scale detailed below)
- Surgeon experience (detailed questionnaire available in Appendix B)

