8.1.3 Causality Assessment

The investigator's assessment of causality must be provided for all adverse events (serious and non-serious). An investigator's causality assessment is the determination of whether there exists a reasonable possibility that the investigational product caused or contributed to an adverse event. If the investigator's final determination of causality is unknown and the investigator does not know whether or not investigational product caused the event, then the event will be handled as "related to investigational product" for reporting purposes. If the investigator's causality assessment is "unknown but not related to investigational product", this should be clearly documented on trial records. In addition, if the investigator determines a serious adverse event is associated with trial procedures, the investigator must record this causal relationship in the source documents and eCRF, as appropriate, and report such an assessment in accordance with the serious adverse event reporting requirements, if applicable.

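### Section 8.1.1 says the expected complications have no direct link to the device, which conflicts with sections 4.1.2 and 5.1 and may tilt causality judgements towards not related

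*Combined protocol and SAP*

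**What the plan says.** Section 8.1.1 reasons from a premise, "As the use of the HoloLens has no direct impact on the workflow of the standard surgical procedure", to an expectation, "we do not expect it to cause any adverse events whatsoever". It then says that complications of the kind seen in standard care are expected, but that "none of these complications are directly linked to the use of the device". The same section also says "The investigator is required to assess causality".

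Section 4.1.2 describes what the device does. The entry point rests on the pathology, anatomical knowledge, "surgical planning information based on the preoperative CT scan, as well as the augmented reality-displayed surgical trajectory". At the next step "a drill trajectory is made in the skull, following the predefined trajectory that the drain should follow", and that trajectory is again based on several inputs "and, importantly, the augmented reality-displayed surgical trajectory".

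Section 5.1 lists better complication and revision rates with AR among the secondary endpoints. Section 8.1.3 asks, for every adverse event, whether there is a reasonable possibility that the product caused or contributed to it. Unknown causality is handled as related for reporting. A further category, "unknown but not related to investigational product", must be clearly documented if used.

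**The concern.** An unchanged workflow is not evidence that a causal path is absent. A poorly registered overlay can shift an entry point or an angle while every surgical step stays the same. Section 8.1.1 nonetheless moves from no effect on workflow to no adverse events, and then to no direct link with the complications expected.

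Safety is one of the three stated aims in the opening of section 5. The causality judgement belongs to the investigator, and the software comes from the consortium running the project. Section 9.1 mentions an independent data monitoring committee but gives it no role in causality. A protocol statement that leans one way therefore has no described counterweight. In a study this small, one reclassified event can change what is reported about the device.

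**Working it through.** No stated figure underlies this point, so the check is mainly a comparison of sections, followed by a scale calculation.

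**1. Does the premise support the conclusion?** Section 8.1.1 relies on unchanged workflow. Section 4.1.2 has the displayed trajectory informing both the entry point and the drill path. Both can be true, but the second supplies a route to harm that the first does not exclude. Overlay error is not hypothetical in the protocol's own phantom data: Table 1-2 in section 1.2.3 puts 7% of localisations with the tracked system 5-10 mm off. That shows error exists on a phantom. It does not show harm in patients.

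**2. Which complications are covered?** Section 1.3 counts malplacement, post-placement haemorrhage and drain-related infection in the overall EVD complication rate. Placement grade is also the primary endpoint. Poor placement, the very outcome the device is meant to change, is thus among the complications that 8.1.1 calls not directly linked.

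**3. Is the direction consistent?** Section 5.1 presumes that AR can lower complication and revision rates. A device able to lower them could in principle raise them. Elsewhere the protocol allows for hazards: section 5.1 lists inattentional blindness for exploration, and Appendix B (item 6) asks surgeons whether the system may affect patient safety adversely.

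**4. Is the standard the same?** Section 8.1.1 speaks of a direct link. Section 8.1.3 uses caused or contributed, which is wider. An overlay error that adds to a misplacement would meet the second test and might be thought to fail the first.

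**5. What depends on the causality call?**

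| Item | Depends on causality? | Section |
|---|---|---|
| Capture of adverse events | No | 8.1, 8.1.1 |
| Serious-event notification up to first follow-up | No | 8.2 |
| Complication and revision rate endpoints | No | 5.1 |
| Count of events recorded as device-related | Yes | 8.1.3 |
| Serious events after the reporting period | Yes | 8.2 |
| Follow-up of device-related events to resolution or stability | Yes, mainly non-serious ones | 8.1.1 |

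The last row is limited to mainly non-serious events because section 4.2 already follows serious events until they resolve or are judged chronic or stable.

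**6. Scale.** Inputs: complication rate p = 14.2% to 16.1% (section 1.3, without AR) and n = 10 to 15 (section 5.2). Expected count = n × p; chance of at least one = 1 − (1 − p)^n, assuming independent patients.

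- n = 10: 10 × 0.142 = 1.42 and 10 × 0.161 = 1.61. Chance of at least one: 1 − 0.858^10 = 78% and 1 − 0.839^10 = 83%.
- n = 15: 15 × 0.142 = 2.13 and 15 × 0.161 = 2.42. Chance of at least one: 1 − 0.858^15 = 90% and 1 − 0.839^15 = 93%.

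Moving one patient between related and not related changes the device-related proportion by 1/15 = 6.7 to 1/10 = 10 percentage points.

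**The case against.** A reader might infer that 8.1.1 settles every causality assessment in advance, that the device-related rate is therefore zero by construction, and that notification of a real overlay fault would be delayed. The documents do not support this.

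- The wording is an expectation about background complications of standard care. It is not a classification rule.
- The same section requires the investigator to assess causality. Section 8.1.3 requires this for every event, on a wide standard, with unknown handled as related. Section 4.2 also has the relationship to the procedure or trial intervention recorded.
- Notification of serious events up to the first follow-up appointment carries no causality condition.
- The harms most at issue are largely measured without attribution: placement on CT within 24 hours, number of passes, and the complication rate.
- AR is one of several inputs to the trajectory.
- The 1.4 to 2.4 figure is the count expected with no device effect, and it includes infections, for which an overlay error is a less plausible cause. It does not measure misclassification.

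All of this stands, and it limits the point to a possible bias in judgement. It does not remove the conflict between 8.1.1 and 4.1.2 or the difference in standard from 8.1.3. The default to related protects only an investigator who regards causality as unknown. One who accepts 8.1.1 may not get that far.

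**Conclusion.** The conflict is real and worth correcting, but its reach is limited. Section 8.1.1 makes a prior statement that sections 4.1.2 and 5.1 do not support, and it uses a narrower notion of causation than 8.1.3. The likely effect is a lean towards not related in a small number of judgements. The consequences are confined to the device-related tally, serious events after the reporting period, and the length of follow-up for mainly non-serious device-related events.

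The size of the bias cannot be computed from the documents. What can be said is that at least one complication is likely (78-93%) if the literature rate without AR applies and patients are independent, and that one judgement shifts the related proportion by 6.7 to 10 percentage points. The conclusion assumes that investigators read 8.1.1 as guidance when they complete the causality field, which is plausible but not shown.

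**What to change.** 1. Delete the two statements in 8.1.1, on expecting no device-caused events and on the absence of a direct link, and reconcile the section with 4.1.2 and 8.1.3.
2. Name malplacement, multiple passes, post-placement haemorrhage and revision as events for which a device contribution must be explicitly considered under the 8.1.3 standard. It should not be presumed: section 1.3 cites 7-13% poor placement and 5.4% multiple passes without AR. Where multiple passes or a revision is not itself an adverse event, attach the assessment to the outcome record or to the event that led to it.
3. Before any of these is classed as not related, record a short reason, checked where available against the HoloLens footage that section 9.2 already plans to review.

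The cost is an edit to the protocol and a brief note per event. Some events will be recorded as possibly related that would otherwise not have been. No new data collection is needed.
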